#### Protocol-Required Laboratory Assessments

Laboratory Assessments	Parameters		
Hematology	Platelet count Red blood cell (RBC) count Hemoglobin Hematocrit	RBC Indices: Mean Corpuscular Volume (MCV) Mean Corpuscular Hemoglobin (MCH) % Reticulocytes	White blood cell (WBC) count with Differential: Neutrophils Lymphocytes Monocytes Eosinophils Basophils
	Note: A WBC evaluation may include any abnormal cells, which will then be reported by the laboratory. An RBC evaluation may include abnormalities in the RBC count, RBC parameters, or RBC morphology, which will then be reported by the laboratory. In addition, any other abnormal cells in a blood smear will also be reported.		
Clinical Chemistry	Sodium Potassium Chloride Bicarbonate Blood urea nitrogen Creatinine Glucose (non-fasting) Aspartate aminotransferase (AST)/Serum glutamic-oxaloacetic Alanine aminotransferase (ALT)/Serum glutamic-oxaloacetic Gamma-glutamyltransferase estimated glomerular filtration rate (eGFR) high-sensitivity C reactive protein (hsCRP)	Total bilirubin (Tbili) and Direct bilirubin Alkaline phosphatase Creatine phosphokinase (CPK) Lactic acid dehydrogenase (LDH) Uric acid Calcium Phosphate Albumin Total protein Cholesterol Triglycerides Magnesium	
	Details of liver chemistry stopping criteria and required actions and follow-up are given in Appendix 5: Liver Safety: Suggested Actions and Follow-up Assessments . Possible Hy's Law case (ALT or AST $\geq 3 \times$ ULN and Tbili $\geq 2 \times$ ULN) reporting requirements are defined in Section 8.4.1.		
Lipid Panel	Total cholesterol High-density lipoprotein (HDL) Low-density lipoprotein (LDL; calculated) Triglycerides		
	Note: Fasting requirements are described in the SoA (Section 1.3).		

Laboratory Assessments	Parameters	
Routine Urinalysis	Dipstick Specific gravity pH Glucose Protein Blood Ketones Bilirubin Urobilinogen Nitrite Leukocyte esterase	Sediment (if dipstick result is abnormal) RBC WBC Epithelial cells Crystals Casts Bacteria
	If dipstick result is abnormal, microscopy will be used to measure sediment.  In the microscopic examination, observations other than the presence of WBC, RBC and casts may also be reported by the laboratory.	

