6.7. Appendix 7 Laboratory Toxicity Grading

The grading scale use for lab assessments is based on 'NCI-CTCAE v5.0'.

If a laboratory value falls within the grading as specified below but also within the laboratory normal limits, the value is considered to be normal and will be reset to grade 0.

Prebaseline measurements will use the same grading ranges as applied to baseline measurements. In case a test has two sets of ranges – one for baseline normal and one for baseline abnormal, the one for baseline normal will be applied for all measurements taken prebaseline and on baseline.

Text in gray italic in the table is present in the grading scale, but is not applied by Janssen when grading lab data.

CTCAE Term	Grade 1	Grade 2	Grade 3	Grade 4	Janssen Implementation Notes
Blood and lymphatic system disorders					
Anemia	Hemoglobin (Hgb) <LLN - 10.0 g/dL; <LLN - 6.2 mmol/L; <LLN - 100 g/L	Hemoglobin (Hgb) <10.0 - 8.0 g/dL; <6.2 - 4.9 mmol/L; <100 - 80g/L	Hemoglobin (Hgb) <8.0 g/dL; <4.9 mmol/L; <80 g/L; transfusion indicated	Life-threatening consequences; urgent intervention indicated	Clinical signs and symptoms are not taken into consideration for grading.
Leukocytosis	-	-	>100,000/mm ³ ; >100 x 10 ⁹ /L	Clinical manifestations of leucostasis; urgent intervention indicated	Clinical signs and symptoms are not taken into consideration for grading; Added ranges in SI unit (x 10 ⁹ /L)
Investigations					
Activated partial thromboplastin time prolonged	>ULN - 1.5 x ULN	>1.5 - 2.5 x ULN	>2.5 x ULN; bleeding	-	Clinical signs and symptoms are not taken into consideration for grading.
Alanine aminotransferase increased	>ULN - 3.0 x ULN if baseline was normal; 1.5 - 3.0 x baseline if baseline was abnormal	>3.0 - 5.0 x ULN if baseline was normal; >3.0 - 5.0 x baseline if baseline was abnormal	>5.0 - 20.0 x ULN if baseline was normal; >5.0 - 20.0 x baseline if baseline was abnormal	>20.0 x ULN if baseline was normal; >20.0 x baseline if baseline was abnormal	Ranges defined for “abnormal baseline” are applied only if baseline > ULN. If baseline < ULN, then ranges for “normal baseline” are applied.

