Alkaline phosphatase increased	>ULN - 2.5 x ULN if baseline was normal; 2.0 - 2.5 x baseline if baseline was abnormal	>2.5 - 5.0 x ULN if baseline was normal; >2.5 - 5.0 x baseline if baseline was abnormal	>5.0 - 20.0 x ULN if baseline was normal; >5.0 - 20.0 x baseline if baseline was abnormal	>20.0 x ULN if baseline was normal; >20.0 x baseline if baseline was abnormal	Ranges defined for “abnormal baseline” are applied only if baseline > ULN. If baseline < LLN, then ranges for “normal baseline” are applied.
Aspartate aminotransferase increased	>ULN - 3.0 x ULN if baseline was normal; 1.5 - 3.0 x baseline if baseline was abnormal	>3.0 - 5.0 x ULN if baseline was normal; >3.0 - 5.0 x baseline if baseline was abnormal	>5.0 - 20.0 x ULN if baseline was normal; >5.0 - 20.0 x baseline if baseline was abnormal	>20.0 x ULN if baseline was normal; >20.0 x baseline if baseline was abnormal	Ranges defined for “abnormal baseline” are applied only if baseline > ULN. If baseline < LLN, then ranges for “normal baseline” are applied.

CTCAE Term	Grade 1	Grade 2	Grade 3	Grade 4	Janssen Implementation Notes
Blood bilirubin increased	>ULN - 1.5 x ULN if baseline was normal; > 1.0 - 1.5 x baseline if baseline was abnormal	>1.5 - 3.0 x ULN if baseline was normal; >1.5 - 3.0 x baseline if baseline was abnormal	>3.0 - 10.0 x ULN if baseline was normal; >3.0 - 10.0 x baseline if baseline was abnormal	>10.0 x ULN if baseline was normal; >10.0 x baseline if baseline was abnormal	Ranges defined for “abnormal baseline” are applied only if baseline > ULN. If baseline < LLN, then ranges for “normal baseline” are applied.
CD4 lymphocytes decreased	<LLN - 500/mm ³ ; <LLN - 0.5 x 10 ⁹ /L	<500 - 200/mm ³ ; <0.5 - 0.2 x 10 ⁹ /L	<200 - 50/mm ³ ; <0.2 x 0.05 - 10 ⁹ /L	<50/mm ³ ; <0.05 x 10 ⁹ /L	
Cholesterol high	>ULN - 300 mg/dL; >ULN - 7.75 mmol/L	>300 - 400 mg/dL; >7.75 - 10.34 mmol/L	>400 - 500 mg/dL; >10.34 - 12.92 mmol/L	>500 mg/dL; >12.92 mmol/L	
CPK increased	>ULN - 2.5 x ULN	>2.5 x ULN - 5 x ULN	>5 x ULN - 10 x ULN	>10 x ULN	CPK (Creatine Phosphokinase) and CK (Creatine Kinase) are synonyms
Creatinine increased	>ULN - 1.5 x ULN	>1.5 - 3.0 x baseline; >1.5 - 3.0 x ULN	>3.0 x baseline; >3.0 - 6.0 x ULN	>6.0 x ULN	

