CTCAE Term	Grade 1	Grade 2	Grade 3	Grade 4	Janssen Implementation Notes
Hypomagnesemia	Magnesium <LLN - 1.2 mg/dL; <LLN - 0.5 mmol/L	Magnesium <1.2 - 0.9 mg/dL; <0.5 - 0.4 mmol/L	Magnesium <0.9 - 0.7 mg/dL; <0.4 - 0.3 mmol/L	Magnesium <0.7 mg/dL; <0.3 mmol/L; life-threatening consequences	Clinical signs and symptoms are not taken into consideration for grading.
Hyponatremia	Sodium <LLN – 130 mmol/L	Sodium 125-129 mmol/L and asymptomatic	Sodium 125-129 mmol/L symptomatic; 120-124 mmol/L regardless of symptoms	Sodium <120 mmol/L; life-threatening consequences	Clinical signs and symptoms are not taken into consideration for grading. Worst case (“<130-120 mmol/L” for grade 3 added by Janssen) is applied across grade 2/3 ranges: 120-129 mol/L assigned to grade 3, grade 2 not used.
Renal and urinary disorders					
Proteinuria	1+ proteinuria; urinary protein \geq ULN - <1.0 g/24 hrs; urinary protein \geq ULN - <1000 mg/day	Adult: 2+ and 3+ proteinuria; urinary protein 1.0 - <3.5 g/24 hrs; urinary protein 1000 - <3500 mg/day Pediatric: Urine P/C (Protein/Creatinine) ratio 0.5 - 1.9; Urine P/C (Protein/Creatinine) 56.5 – 214.7 g/mol	Adult: 4+ proteinuria; urinary protein \geq 3.5 g/24 hrs; urinary protein \geq 3500 mg/day; Pediatric: Urine P/C (Protein/Creatinine) ratio >1.9; Urine P/C (Protein/Creatinine) >214.7 g/mol	-	In case both 24-h urine collection and dipstick are collected, then worst case is taken, as opposed to having 24-h urine collection take precedence over dipstick. Added ranges in SI unit for urinary protein (mg/day) and for urine P/C (g/mol). Pediatric grading is applied to age range [0-18]. Adult grading is applied for ages [>18].

* Grade 0 is assigned to a lab assessment when the lab test is described in the table, but the lab value is not assigned a grade 1 or high

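### SAP Appendix 7 gives Grade 0 to dipstick protein of 2+ to 4+ at age 18 or under, so no participant of that age can enter the Grade 2 or higher listing for proteinuria

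*SAP*

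**What the plan says.** SAP section 6.7 (Appendix 7) holds the laboratory grading table. A general rule at its head deals with in-range results: "If a laboratory value falls within the grading as specified below but also within the laboratory normal limits", then "the value is considered to be normal and will be reset to grade 0". A footnote at the end deals with whatever is left over: "Grade 0 is assigned to a lab assessment when the lab test is described in the table" and the value has earned no higher grade.

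The proteinuria row reads as follows.

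- Grade 1 opens with "1+ proteinuria; urinary protein" and carries no age label.
- Grade 2 is 2+ and 3+ on dipstick (or a 24-hour protein band) for adults. For pediatric participants it is a urine protein/creatinine ratio of 0.5 to 1.9.
- Grade 3 is 4+ on dipstick (or a 24-hour protein threshold) for adults. For pediatric participants it is a ratio above 1.9.
- The implementation note sets the age split: "Pediatric grading is applied to age range [0-18]. Adult grading is applied for ages [>18".

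On the data side, Protocol section 10.1 (Appendix 1) lists protein among the dipstick items. It lists neither a urine protein/creatinine ratio nor a 24-hour collection. The only follow-up it gives for an abnormal dipstick is of another kind: "If dipstick result is abnormal, microscopy will be used to measure sediment".

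SAP section 4.5.3.1 uses the grades in two outputs: a worst-grade shift summary for chemistry and hematology, and a listing of participants at Grade 2 or higher. It also lists all laboratory parameters.

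**The concern.** A toxicity scale should not fall as the finding gets worse. Here, at age 18 or under, it rises from negative to 1+ and then drops back to Grade 0 for 2+, 3+ and 4+. The cause is a mismatch between the table and the trial's tests: the pediatric criteria need a ratio that the listed panel does not contain, and the dipstick criteria the trial could use are reserved for adults.

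At stake is the Grade 2 or higher listing, which is meant to pick out participants whose results deserve a look. Participants may enter from age 12 (Protocol section 5.1), and SAP section 4.8 drops the listing of markedly abnormal laboratory results. SAP section 4.5.3.1 plans no descriptive or shift summary for urinalysis, so in the SAP the toxicity grade is the one threshold-based flag for urine protein. For the youngest participants it cannot be raised.

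**Working it through.** No sample size, power or test is involved. The check is to apply the rules of Appendix 7, in order, to each dipstick result that the trial can produce.

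**Inputs**

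1. Possible readings: negative, 1+, 2+, 3+, 4+ (SAP Appendix 7; dipstick protein is in Protocol Appendix 1).
2. Grade 1: 1+, any age (proteinuria row).
3. Grades 2 and 3 above age 18: 2+/3+ and 4+ respectively (same row).
4. Grades 2 and 3 at ages 0 to 18: protein/creatinine ratio only (same row).
5. Ratio available: no (Protocol Appendix 1 panel).
6. No grade reached: Grade 0 (footnote).

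**Result**

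| Dipstick | Above 18 | 18 or under | Why, at 18 or under |
|---|---|---|---|
| negative | 0 | 0 | footnote |
| 1+ | 1 | 1 | Grade 1 has no age label |
| 2+ | 2 | 0 | adult label; no ratio; footnote |
| 3+ | 2 | 0 | same |
| 4+ | 3 | 0 | same |

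The in-range reset plays no part, because a 2+ to 4+ reading is not a normal result. The footnote alone produces the zeros.

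**Does a kinder reading help?** A programmer might treat 1+ as meaning 1+ or more when nothing higher applies. The sequence at 18 or under would then be 0, 1, 1, 1, 1. It no longer falls, but it still never reaches Grade 2, so the listing is affected in the same way.

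**Age boundary.** Protocol section 8.2 gives the adult quality-of-life instrument to those aged 18 or more on the first date of screening, and the children's version to those from 12 to under 18. Appendix 7 counts 18 as pediatric. If age is held in completed years, an 18-year-old is an adult elsewhere in the trial and pediatric for this one grade. Appendix 7 also does not say whether age is taken at screening or at the sample.

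**Reach.** The shift summary covers chemistry and hematology only, so proteinuria does not enter it. That leaves the Grade 2 or higher listing.

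**The case against.** The practical loss is small, and most of that case stands. Every dipstick result is still in the full laboratory listing. Protocol section 8.3.3 has the investigator review laboratory results and record clinically relevant changes as adverse events whatever their grade. Protocol section 9.3.5 also promises a listing of results outside the reference range; the SAP does not repeat it but does not list it as dropped. About 16 participants are planned, so a reader can go through the raw listing. SAP section 4.1 allows for no adolescent enrolling, in which case only an 18-year-old could be affected. The table is also a generic one: it carries tests absent from Protocol Appendix 1, such as lipase and haptoglobin, so an unused ratio criterion is no error in itself. None of this makes the sequence 0, 1, 0, 0, 0 a sensible grading.

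A reader might infer a second defect of the same kind, for creatinine. That row grades a rise over baseline (">1.5 - 3.0 x baseline; >1.5 - 3.0 x ULN" for Grade 2, ">3.0 x baseline; >3.0 - 6.0 x ULN" for Grade 3), and the in-range reset overrides it. The mechanics are right. With an assumed upper limit of 0.80 mg/dL, a rise from 0.40 to 0.79 is 0.79/0.40 = 1.98 times baseline, Grade 2 by the row and Grade 0 after the reset. The documents do not support calling it an error, for three reasons.

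- The reset is an explicit convention applied to every test.
- Exempting creatinine is a trade-off. At the same assumed limit, 0.40 to 0.61 (1.53 times baseline, in range) would become Grade 2. Yet 0.79 to 1.15 (1.46 times baseline, 1.44 times the limit, out of range) would stay Grade 1.
- Appendix 7 says that text in gray italic is not applied. Whether the baseline multiple in the creatinine row is so marked could not be confirmed from the available text.

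The SAP also plans change from baseline for chemistry, and creatinine and eGFR are both in that panel.

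**Conclusion.** The proteinuria point holds and is minor. As written, Appendix 7 assigns Grade 0 to 2+, 3+ and 4+ dipstick protein at age 18 or under, where the adult scale gives 2, 2 and 3. No such participant can appear in the Grade 2 or higher listing for proteinuria.

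It would be too much to infer that renal findings would be hidden from the report. One listing is affected, no endpoint or estimand depends on it, and the raw values remain.

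The conclusion rests on four assumptions: that the laboratory manual, to which Protocol Appendix 1 leaves further detail, does not add a protein/creatinine ratio; that urinalysis results are graded and feed the listing; that someone aged 18 or under enrols; and, for the 18-year-old boundary, that age is held in completed years. The creatinine reset is not part of the conclusion, and no change to it is needed.

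**What to change.** In the proteinuria row of SAP Appendix 7, apply the dipstick cut points to all ages (2+ and 3+ as Grade 2, 4+ as Grade 3), since the ratio that the pediatric criteria need is not in the listed panel. If any age split is kept, set it at under 18 versus 18 and over, and state that age is taken on the first date of screening, as for the quality-of-life instruments.

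The sequence at every age then becomes 0, 1, 2, 2, 3. The cost is about one line of SAP text and minor programming, with no new data collection. A few more Grade 2 or 3 proteinuria entries may appear in the listing.

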4.5.3. Additional Safety Assessments

4.5.3.1. Clinical Laboratory Tests

Descriptive statistics will be presented for selected chemistry, hematology laboratory tests at scheduled time points.

Change/percent change from baseline will be summarized for chemistry, hematology tests and displayed. A box plot of laboratory measurements and change from baseline will be provided.

Applicable laboratory results will be graded according to NCI-CTCAE version 5.0.

Shift summaries from baseline laboratory value to the worst NCI-CTCAE, version 5.0 grade in chemistry and hematology tests with NCI-CTCAE, version 5.0 will be presented.

All laboratory parameters and the participants with toxicity grade ≥ 2 will be listed.

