Fibrinogen decreased	<1.0 - 0.75 x LLN; if abnormal, <25% decrease from baseline	<0.75 - 0.5 x LLN; if abnormal, 25 - <50% decrease from baseline	<0.5 - 0.25 x LLN; if abnormal, 50 - <75% decrease from baseline	<0.25 x LLN; if abnormal, 75% decrease from baseline; absolute value <50 mg/dL	Ranges defined for “abnormal” are applied only on values < LLN. Grade 0 will be assigned to values > ULN.
GGT increased	>ULN - 2.5 x ULN if baseline was normal; 2.0 - 2.5 x baseline if baseline was abnormal	>2.5 - 5.0 x ULN if baseline was normal; >2.5 - 5.0 x baseline if baseline was abnormal	>5.0 - 20.0 x ULN if baseline was normal; >5.0 - 20.0 x baseline if baseline was abnormal	>20.0 x ULN if baseline was normal; >20.0 x baseline if baseline was abnormal	Ranges defined for “abnormal baseline” are applied only if baseline > ULN. If baseline < LLN, then ranges for “normal baseline” are applied.
Haptoglobin decreased	<LLN	-	-	-	
Hemoglobin increased	Increase in >0 - 2 g/dL; Increase in >0 - 20 g/L	Increase in >2 - 4 g/dL; Increase in >20 - 40 g/L	Increase in >4 g/dL; Increase in >40 g/L	-	The increase indicates the level of increase above normal (above ULN). Applied as, eg, grade 1 (g/dL): >ULN - ULN+2 g/dL; Added ranges in SI unit (g/L).

CTCAE Term	Grade 1	Grade 2	Grade 3	Grade 4	Janssen Implementation Notes
INR increased	>1.2 - 1.5; >1 - 1.5 x baseline if on anticoagulation; monitoring only indicated	>1.5 - 2.5; >1.5 - 2.5 x baseline if on anticoagulation; dose adjustment indicated	>2.5; >2.5 x baseline if on anticoagulation; bleeding	-	Concomitant therapy or clinical signs and symptoms are not taken into consideration for grading.
Lipase increased	>ULN - 1.5 x ULN	>1.5 - 2.0 x ULN; >2.0 - 5.0 x ULN and asymptomatic	>2.0 - 5.0 x ULN with signs or symptoms; >5.0 x ULN and asymptomatic	>5.0 x ULN and with signs or symptoms	“Asymptomatic” ranges are not taken into consideration for grading, ie, worst case grading is applied.
Lymphocyte count decreased	<LLN - 800/mm3; <LLN - 0.8 x 10e9/L	<800 - 500/mm3; <0.8 - 0.5 x 10e9 /L	<500 - 200/mm3; <0.5 - 0.2 x 10e9 /L	<200/mm3; <0.2 x 10e9 /L	
Lymphocyte count increased	-	>4000/mm3 - 20,000/mm3; >4 - 20 x 10e9 /L	>20,000/mm3; >20 x 10e9 /L	-	Added ranges in SI unit (x 10e9 /L).
Neutrophil count decreased	<LLN - 1500/mm3; <LLN - 1.5 x 10e9 /L	<1500 - 1000/mm3; <1.5 - 1.0 x 10e9 /L	<1000 - 500/mm3; <1.0 - 0.5 x 10e9 /L	<500/mm3; <0.5 x 10e9 /L	Both Neutrophils and segmented neutrophils are graded using these criteria.

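### The liver-test shift table grades baseline on ×ULN but later values on multiples of an abnormal baseline, so an unchanged abnormal value is Grade 0 like a normalised one, and no output categorises ALT/AST by ×ULN

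*SAP*

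**What the plan says.** SAP Appendix 7 (Section 6.7) gives two sets of ranges for ALT, AST, ALP, GGT and bilirubin, one for a normal and one for an abnormal baseline. For values at or before baseline, "the one for baseline normal will be applied for all measurements taken prebaseline and on baseline". The abnormal-baseline ranges apply after baseline when the baseline value is above ULN. They are multiples of the participant's own baseline. Grade 1 is:

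- ALT and AST: "1.5 - 3.0 x baseline if baseline was abnormal"
- ALP and GGT: "2.0 - 2.5 x baseline if baseline was abnormal"
- bilirubin: "> 1.0 - 1.5 x baseline if baseline was abnormal"

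Grade 0 arises in two ways. If a value is within the laboratory's normal limits, "the value is considered to be normal and will be reset to grade 0". The footnote to the table also gives Grade 0 when the test is in the table "but the lab value is not assigned a grade 1 or high".

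SAP 4.5.3.1 plans "Shift summaries from baseline laboratory value to the worst NCI-CTCAE, version 5.0 grade", and a listing of all laboratory parameters and of participants at Grade 2 or higher.

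Protocol 9.3.5 says that both CTCAE and ULN will serve to identify abnormal results, and it defines the Grade 2+ listing by CTCAE criteria. SAP 4.8 drops the protocol's incidence and severity summary and its markedly abnormal listing. The reason given is that few patients are enrolled and the information can be read from the summary table and the list.

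**The concern.** The measuring scale changes at the first dose, but only for participants who enter with an abnormal value. For them, a post-baseline Grade 0 can mean that the test normalised, that it stayed abnormal at the same level, or (except for bilirubin) that it rose by a sizeable fraction. A reader of the shift table cannot tell which.

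The same scale also decides who reaches Grade 2. The protocol's liver monitoring and stopping tiers (Protocol Appendix 5) are multiples of ULN, and the SAP plans no table or listing by those multiples. The shift table is the only categorised laboratory table in SAP 4.5.3.1. With a target of 8 participants per disease group, one participant is 1/8 = 12.5% of a column.

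**Working it through.** The documents give no figure to reproduce here, so the check applies the Appendix 7 ranges directly.

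**Inputs.** Let b = baseline/ULN, x = post-baseline value/ULN and r = x/b. All ranges are from SAP Appendix 7.

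| Test | Baseline grades 1 / 2 / 3 (on b) | Later grades 1 / 2 / 3 if b > 1 (on r) |
|---|---|---|
| ALT, AST | >1–3 / >3–5 / >5–20 | 1.5–3 / >3–5 / >5–20 |
| ALP, GGT | >1–2.5 / >2.5–5 / >5–20 | 2–2.5 / >2.5–5 / >5–20 |
| Bilirubin | >1–1.5 / >1.5–3 / >3–10 | >1–1.5 / >1.5–3 / >3–10 |

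A later value is Grade 0 if it is normal or if r is below the Grade 1 range.

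**Step 1: the shift table.** Each row takes x as the participant's worst later value.

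| Test | b | x | r | Baseline grade | Later grade (SAP) | Later grade (ULN ranges) |
|---|---|---|---|---|---|---|
| ALT/AST | 1.9 | 0.9 | normal | 1 | 0 | 0 |
| ALT/AST | 1.9 | 1.9 | 1.00 | 1 | 0 | 1 |
| ALT/AST | 1.9 | 2.8 | 1.47 | 1 | 0 | 1 |
| GGT | 3.0 | 3.0 | 1.00 | 2 | 0 | 2 |
| GGT | 3.0 | 5.9 | 1.97 | 2 | 0 | 3 |
| Bilirubin | 1.4 | 1.4 | 1.00 | 1 | 0 | 1 |
| Bilirubin | 1.4 | 1.5 | 1.07 | 1 | 1 | 1 |
| Bilirubin | 1.6 | 2.3 | 1.44 | 2 | 1 | 2 |

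An unchanged abnormal value (r = 1) is Grade 0 for all five tests. A rise stays at Grade 0 up to just under 1.5× baseline for ALT/AST and just under 2× for ALP/GGT. For bilirubin any rise is graded, so a rise can look like improvement only from baseline Grade 2 or higher (last row).

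The SAP does not say what the baseline axis of the shift table is. If it is baseline grade, which is the natural reading because Appendix 7 says how to grade baseline, the second and third rows show as a shift from 1 to 0. If it is normal/high, they fall in the same high-to-Grade-0 cell as the first row.

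**Step 2: ALT/AST against the protocol's ×ULN tiers.** With b > 1, Grade 1 extends to x = 3b. Protocol 5.2 excludes ALT or AST above 2×ULN at screening, so take b up to 2.0. The share of the 3–5×ULN tier (width 2) that is only Grade 1 is (min(5, 3b) − 3)/2. For the 5–8×ULN tier (width 3) it is (min(8, 3b) − 5)/3, with a floor of 0.

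| b | Top of Grade 1, 3b (×ULN) | Share of 3–5 tier | Share of 5–8 tier |
|---|---|---|---|
| 1.1 | 3.3 | 0.3/2 = 15% | 0% |
| 1.5 | 4.5 | 1.5/2 = 75% | 0% |
| 1.67 | 5.0 | 100% | 0% |
| 1.9 | 5.7 | 100% | 0.7/3 = 23% |
| 2.0 | 6.0 | 100% | 1.0/3 = 33% |

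These percentages are shares of interval width. They are not probabilities or participant counts. The 5×ULN case needs 3b > 5, that is, b above 5/3 ≈ 1.67. Two examples:

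- 1.2 to 3.5×ULN: r = 2.92, Grade 1 (Grade 2 on ULN ranges)
- 1.9 to 5.6×ULN: r = 2.95, Grade 1 (Grade 3 on ULN ranges)

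At x = 8 and b = 2.0, r = 4.0, which is Grade 2. So with b up to 2.0, no value of 8×ULN or more falls below Grade 2.

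**The case against.** The strongest reply is that this is a choice of scale. Multiples of baseline show change from an abnormal starting point, while multiples of ULN count a stable prior elevation as a post-baseline grade. Methotrexate, a retinoid or cyclosporine may continue at a stable dose (Protocol 5.1 and 6.9.1.1), so separating prior abnormality from change is a reasonable aim. That stands as a reason to keep baseline-relative grades somewhere. It does not justify one table with ULN grades on one side and baseline-relative grades on the other.

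A reader might infer that the Grade 2+ listing wrongly omits participants. The documents do not support this: Protocol 9.3.5 sets that listing on CTCAE criteria and the SAP follows it. What remains is that the same protocol section also names ULN, and no SAP output is categorised by it.

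A reader might also infer that the shift table will certainly show false improvement. That depends on an unstated axis; on the other reading the fault is pooling.

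The information is not lost. All laboratory values are listed. SAP 4.5.3.1 adds that "Change/percent change from baseline will be summarized for chemistry, hematology tests and displayed", with box plots. SAP 4.5.2.1 lists possible Hy's Law cases, which the protocol defines by ULN. The protocol's listing of out-of-range results is not among the items dropped in SAP 4.8. With 16 participants, looking up individual values is quick. This limits the severity. However, an isolated ALT rise to 5.6×ULN is not a possible Hy's Law case, which also needs raised bilirubin or INR, so that listing does not fill the gap.

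**Conclusion.** The point holds as a minor reporting defect. For participants with a baseline above ULN in any of the five tests, the shift table cannot separate a normalised value from an unchanged abnormal one or, outside bilirubin, from a moderate rise. ALT/AST values above 3×ULN (any baseline above ULN), or from 5 to 6×ULN (baseline about 1.67 to 2.0×ULN), can be Grade 1. They are then individually visible only in the full laboratory listings, unless another reporting route picks them up. The reason given in SAP 4.8 for dropping other laboratory summaries is weaker for these participants: the list serves, but the categorised table does not.

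The documents do not support a participant-safety problem, because monitoring and stopping use ×ULN directly. No efficacy result is touched.

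Two assumptions matter. The 2×ULN limit applies at screening, while the safety baseline is the last value before the first dose (SAP 4.1.2), so the figures assume that baseline is also within 2×ULN. The number of participants with an abnormal baseline is not given and may be small.

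**What to change.** 1. In SAP 4.5.3.1, state that the baseline axis of the shift table is baseline grade. In that table, grade baseline and post-baseline ALT, AST, ALP, GGT and bilirubin on the same ULN-based ranges.
2. Keep the Grade 2+ listing on CTCAE grades as the protocol specifies, and label it as baseline-relative for participants whose baseline was above ULN.
3. Add one small table or listing of maximum post-baseline ALT and AST at ≥3, ≥5 and ≥8×ULN, matching the thresholds in Protocol Appendix 5.

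The cost is SAP wording, one derivation change and one small output, with no new data. There are two downsides. One value may carry two grades, so the labels are needed. Stable pre-existing elevations will appear as Grade 1 or higher after baseline; because their baseline is graded on the same scale, the shift table will show them as unchanged.
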